| Number of families ⁶⁰ | Intervention: 361 Control: 199 Total: 560 |
| Number of participants | Intervention: 369 adults, 193 children Control: 203 adults, 101 children Total: 572 adults, 294 children |

⁶⁰ Final numbers reported (post attrition) that we will be analysing, rather than in the entire sample.

Updated sampling calculation (LAs = 10) – Only SF sample and latest assumptions

[figure not shown]

Figure 3 – Sampling calculations

SF Sample Size Calculation Table

| | |
|--------------------------------|------------|
| MDES | 0.446 |
| Alpha Level (α) | 0.05 |
| Two-tailed or One-tailed Test? | Two-tailed |
| Power (1- β) | 0.8 |
| Baseline/Endline correlations | |
| Individuals | 0.6 |
| Families | 0.6 |
| Local authorities | 0.6 |
| Average cluster size | |
| Individuals in families | 1.5 |
| Families in local authorities | 56 |
| Number of local authorities | 10 |
| Intraclass cluster correlation | |
| Families | 0.3 |
| Local authorities | 0.1 |

Assumptions

- 3 level clustering – individual in family in local authority
- Assumed a low ICC for families in terms of family functioning (expect different views)
- Assumed a very low ICC for local authorities in terms of family functioning (some clustering of scores based on shared factors, but not strong)
- Assumed baseline/endline correlations of 0.6 at all levels (unknown)

Figure 4 – SF Sample size calculation table

Outcome measures

Table 3: Primary outcome measures

| Variable | Progress towards personal goals |
|------------|--|
| Measure | Goal Based Outcomes (GBO) ⁶¹ |
| Sample | Parents/carers and children/young people aged 8 and over. The GBO will be administered as part of the Family Outcome Questionnaire at an individual level by keyworkers. There will be an adult version (for use with adults and young people aged over 12) and a child-friendly version (for use with children aged 8 to 12). Total GBO scores will be reported, as well as themed scores. We anticipate theming goals using existing taxonomies from psychotherapy research ^{62,63} and using inductive analysis owing to the novel context for use of the GBO. |
| Time point | Baseline: within the assessment period of the first six weeks of the keyworker working with a family. Midline: at a review point when working with the family. Typically, this is between two to five months of working with the family. Endline: At closure when the keyworker stops working with a family. |

Secondary outcome measures for families:

Table 4: Secondary outcome for families 1

| | |
|----------|---|
| Variable | Family functioning |
| Measure | SCORE-15 Index of Family Functioning and Change ⁶⁴ |

⁶¹ Bradley, J., Murphy, S., Fugard, A. J., Nolas, S. M., & Law, D. (2013). What kind of goals do children and young people set for themselves in therapy? Developing a goals framework using CORC data. *Child and Family Clinical Psychology Review*, 1(1), 8-18.; Law,D.,& Bradley,J.(2015).Goals and Goal Based Outcomes(GBOs): Some Useful Information.(3rd ed.) London: CAMHS Press.

⁶² Mok, W. C., Vainieri, I., & Jacob, J. (2024). Exploring goal taxonomies using the goal-based outcome tool in children and young people's mental health settings. *Counselling and Psychotherapy Research*, 24(2), 472-490.

⁶³ Banwell, E., Salhi, L., Hanley, T., & Facey-Campbell, N. (2023). The use of goal-based outcome measures in digital therapy with adults: What goals are set, and are they achieved?. *Counselling and Psychotherapy Research*, 23(3), 770-780.

| | |
|------------|---|
| Sample | Families – Score-15 is administered at an individual level with the child/young person referred to the keyworkers and at least one parent/carer. Scores are then combined into a composite score for the family. |
| Time point | Baseline: within the assessment period of the first six weeks of the keyworker working with a family. Midline: at a review point when working with the family. Typically this is between two to five months of working with the family. Endline: At closure when the keyworker stops working with a family. |

Table 5: Secondary outcome for families 2

| | |
|------------|--|
| Variable | Therapeutic alliance – relationship between the family and keyworker |
| Measure | The Consultation and Relational Empathy (CARE) measure ⁶⁵ |
| Sample | Children/young people and parents/carers. The CARE measure will be administered at an individual level, for parents/carers and young people ages 11 and older, and a version for children aged 8-11. Scores will not be combined but reported separately Families - 10 questions on the relationship between the family and the keyworker. |
| Time point | Baseline: within the assessment period of the first six weeks of the keyworker working with a family. Midline: at a review point when working with the family. Typically this is between two to five months of working with the family. Endline: At closure when the keyworker stops working with a family. |

Table 6: Secondary outcome for families 3

| | |
|----------|-----------------------------------|
| Variable | Step-up to children's social care |
|----------|-----------------------------------|

| | |
|------------|---|
| Measure | Reasons for closure (local authority closure assessment) “Step up/escalated to statutory children’s services” [binary yes/no]. |
| Sample | Families where keyworker support is ending. |
| Time point | Endline: At closure when the keyworker stops working with a family |

Table 7: Secondary outcome for families 4

| | |
|------------|--|
| Variable | Positive progress made by families at closure |
| Measure | Reasons for closure (local authority closure assessment) “End of casework, positive progress made against all issues” |
| Sample | Families where keyworker support is ending. |
| Time point | Endline: At closure when the keyworker stops working with a family. |

Table 8: Secondary outcome for keyworkers 1

| | |
|------------|--|
| Variable | Professional Wellbeing |
| Measure | Adapted measure of professional wellbeing using Professional Wellbeing Self-Assessment Tool ⁶⁶ and The Social Work Organisational Resilience Diagnostic (SWORD) Tool ⁶⁷ |
| Sample | Keyworkers who are in the pilot |
| Time point | Baseline: at the start of the pilot. For intervention local authorities this will be before the training begins. For control local authorities this will be after they have been trained in use of the family level outcome measures at the start of the pilot. Endline: At the end of the pilot. |

Table 9: Secondary outcome for keyworkers 2

| | |
|------------|--|
| Variable | Practice Quality |
| Measure | Adapted measure of practice using the Systemic Therapy Inventory of Change (STIC) and the Systemic Practice Competency Scale (SPCS) |
| Sample | Keyworkers who are in the pilot |
| Time point | Baseline: at the start of the pilot. For intervention local authorities this will be before the training begins. For control local authorities this will be after they have been trained in use of the family level outcome measures at the start of the pilot. Endline: At the end of the pilot. |

Primary outcome measure

In line with the pilot's theory of change of creating systemic practice supporting families to make meaningful progress towards personal goals, the Goal-Based Outcome (GBO) has been chosen in consultation with the expert working group.⁶⁴ The GBO tool is a way of evaluating progress towards goals in work with children, young people, and their parents and carers. The GBO assesses how far an individual feels they have moved towards reaching a goal that they have set for themselves at the beginning of their support, on a scale between 0 and 10. The measure suggests setting three goals. GBOs are also a tool to facilitate shared decision making and enable more personalised support.⁶⁵ The Family Outcome Questionnaire which includes the GBO questions are included in Annex B.

As the GBO tool is an idiographic outcome measure, the approach to testing psychometric properties differs from traditional measures. An assessment of the GBO's psychometric properties is as follows:

- **Internal consistency** (the degree to which similar items within a scale correlate with each other): There are mixed views on whether internal consistency of goal measures is relevant, given that the goals set may be focussed on the different

⁶⁴ For more information please see: [The Goal-Based Outcome \(GBO\) Tool Guidance](https://www.goals-in-therapy.com/the-gbo-tool) PDF and the dedicated website: <https://www.goals-in-therapy.com/the-gbo-tool>

⁶⁵ Law, D., & Jacob, J. (2015). Goals and Goal Based Outcomes (GBOs): Some useful information. Third Edition. London, UK: CAMHS Press)

areas of change. However, Edbrooke-Childs et al., found evidence of good internal consistency for parent rated goals.⁶⁶

- **Test-retest reliability** (the degree to which the same respondents have the same score after a period of time when goals shouldn't have changed): Acceptable stability over a 6 to 24 week period has been found.⁶⁷
- **Concurrent validity** (the correlation of the measure with others measuring the same concept): Parent and young person reported goals have been found to be significantly moderately correlated with measures of functioning and satisfaction. Using multilevel analysis techniques, moderate convergent validity has been found with measures of wellbeing, self-esteem and depression.
- **Discriminant validity** (the Lack of correlation with opposite concepts): No significant correlations have been found between parent or young person reported GBO and other measures of symptoms.^{68 69} This suggests that goals may capture areas of change not explored by these symptom measures.⁷⁰

The suggested 'meaningful change' level for GBO, based on the principles of the reliable change index, is reported to be 2.45 in a 1-10 scale.⁷¹ As noted earlier, studies using the GBO show large effect sizes ranging from 1.33 to 2.37 (see section on power calculations for references). As this is the first time (to our knowledge) that the GBO is being used in the context of children's social care, this is relatively exploratory, but we hope to see similar effect sizes to this range to demonstrate evidence of promise. We intend to report overall GBO scores across all goals, as well as for themed goals. Goals will be themed using existing taxonomies from psychotherapy research^{72,73}. However, given that this is the first time, to our knowledge, that the GBO is being used in a study of Early Help, we will also generate our own themes inductively from the data. The measure is licensed under creative commons (CC) and therefore, free to use for the delivery and improvement of health and/or social care. It is also currently available in 9 different languages.

⁶⁶ Edbrooke-Childs, J., Jacob, J., Law, D., Deighton, J., & Wolpert, M. (2015). Interpreting standardized and idiographic outcome measures in CAMHS: what does change mean and how does it relate to functioning and experience?. *Child and Adolescent Mental Health*. 20(3), 142-148. <https://doi.org/10.1111/camh.12107>

⁶⁷ Duncan, C., Cooper, M., & Saxon, D. (2022). Test-retest stability, convergent validity, and sensitivity to change for the Goal-Based Outcome tool for adolescents: Analysis of data from a randomized controlled trial. *Journal of Clinical Psychology*. <https://doi.org/10.1002/jclp.23422>

⁶⁸ Edbrooke-Childs, J., Jacob, J., Law, D., Deighton, J., & Wolpert, M. (2015). Interpreting standardized and idiographic outcome measures in CAMHS: what does change mean and how does it relate to functioning and experience?. *Child and Adolescent Mental Health*. 20(3), 142-148. <https://doi.org/10.1111/camh.12107>

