3. Are there **reductions in step-up to statutory support** for families with a keyworker in local authorities that have implemented systemic practice compared to local authorities that have not?
4. Are there **more case closures with positive progress** made by families who have a keyworker in local authorities that have implemented systemic practice compared to local authorities that have not?
5. Do keyworkers in local authorities that have implemented systemic practice have **increased levels of professional wellbeing** compared to keyworkers in local authorities that have not?
6. Do keyworkers in local authorities that have implemented systemic practice have **improved practice quality** compared to keyworkers in local authorities that have not?

Design

The study will use a parallel 1:1 randomised controlled trial design to compare business-as-usual to business-as-usual plus embedded systemic practice. The local authorities in the sample have in common the fact that they currently, or in the last three years, have not implemented systemic practice throughout their keyworker teams. Business-as-usual will be the standard approach to early help/family help as set out in the Supporting Families Programme guidance.⁵¹

Table 1: Systemic practice trial design

| | |
|---|---|
| Trial design, including number of arms | Parallel non-blinded trial 1:1 randomisation |
| Unit of randomisation | Local authority |
| Stratification variables (if applicable) | Local authority structure |
| Primary outcome | Variable: Progress towards personal goals within the Supporting Families Outcome Framework Measure(s) (instrument, scale, source): Goal Based Outcomes (GBO) |

⁵¹ Department for Education and Department for Levelling Up, Housing and Communities. Supporting Families Programme guidance 2022 to 2025: Guidance. <https://www.gov.uk/government/publications/supporting-families-programme-guidance-2022-to-2025>

| | |
|---------------------------------------|--|

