Unfortunately, no validated measure of either was identified. As a result, a set of questions were created to assess systemic practice quality based on the Systemic Therapy Inventory of Change (STIC), and the Systemic Practice Competency Scale (SPCS).

The Systemic Therapy Inventory of Change (STIC) is a multisystemic and multidimensional feedback system that provides therapists feedback about systemic domains of client change in individual, couple, and family therapy over time.

The Systemic Practice Competency Scale (SPCS) provides a structure for the assessment of Systemic Family Practice (SFP) skills to evaluate family therapy sessions as well as training and supervision. It covers 12 areas of systemic family practice: Interpersonal Effectiveness and Development of Therapeutic Alliance; Convening and managing the session; Collaboration; Conveying a Systemic View; Conceptual Integration; Use of Questioning; Feedback; Intervening in Process; Working with Power and difference; Exploring and managing emotions in sessions; Use of change techniques; and incorporating the outside World.

Data collection

Family Outcome Questionnaire

Data for the primary outcome measure (the Goal Based Outcome) and the first two secondary outcome measures (SCORE-15 and CARE measure) will be collected directly from families via an online Family Outcome Questionnaire administered by their keyworker in control and intervention local authorities. All families who are referred to keyworker teams for family support or early help within the timeframe of the pilot will be asked to complete the questionnaire by their keyworker. The questionnaire will form part of the standard assessment, review and closure process with families that keyworkers go through. Families and they will be supported to complete the questionnaire by their keyworker.

Baseline scores will be collected in the assessment period (first six weeks) when the keyworker starts working with a family. Midline scores (at least one) will be collected at a review point. Typically this is between two to five months of working with the family. Endline scores will be collected at closure when the keyworker stops working with a

family, or when the trial ends. Keyworkers will need to work with a family for a minimum of 10 weeks to be included in the trial analysis.

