As a minimum, at least one parent/carer and the child will need to complete the questionnaire at least two timepoints: baseline and at mid or endline. Ideally, all family members (including other carers and children) working with the keyworker will also complete the questionnaire. Keyworkers judgement will be used when deciding whether the child or young person is capable of completing the questionnaire. Versions of each measure have been developed for children aged 8 and over.

The questionnaire will be available online using a link provided to keyworkers, as well as paper versions for practitioners or administrators to upload. All families in the trial will be provided with an easy-read sheet on the outcome measures as part of their privacy notices and online consent form within the outcome questionnaire.

Training, guidance and support will be provided to keyworkers and those supporting data collection in the local authorities. Refresher training and ongoing support will be provided by Coram and the local systemic practitioner. The Family Outcome Questionnaire is included in Annex B.

Supporting Families Data collection

Data for two secondary outcome measures (whether a family has been stepped-up into statutory support and whether a family has been closed with positive progress as part of the Supporting Families Programme) will be collected indirectly from families through data local authorities collect as part of their early help data collection as part of the Supporting Families Programme. Families will consent to this data being provided via their consent forms and local authorities will provide this data as part of the Data Sharing Agreement agreed with each local authority.

To minimise the burden on families and keyworkers and to maximise the analysis that can be undertaken, local authorities will also be asked to provide additional data on the families already collect this data as part of their case management systems provided via DfE's early help dataset.

This additional data is currently being collected at two time points by local authorities:

- 1) In the assessment period when the keyworker first starts to work with a family usually within the first six weeks of working with a family.
- 2) At closure when the keyworker stops working with a family.

Baseline data will include demographic information on:

- Child Date of Birth

- Parent/carers Date of Birth
- Relationship of the parent/carer to the child
- Sex of the child

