- Sex of the parent/carers
- Ethnicity of the child
- Ethnicity of the parent/carers
- Whether the child has a Special Educational Needs (a SEN statement or Education Health and Care Plan)
- Whether the parent/carers have a disability
- The work status of the parent/carers
- Whether the child has English is an Additional Language
- Whether the parent/carers has English is an Additional Language
- The work status of the parent/carers
- Whether the child is eligible for Free School Meals.

Assessment data will also include information collected as part of DfE's early help dataset:

- Family ID
- Date assessment started
- Whether the case is a re-referral
- Whether the case is eligible for the Supporting Families Programme
- Family Need identified from items with the Supporting Families Outcome Framework⁹⁰

Closure data will include information collected as part of DfE's early help dataset:

- Family ID
- Reasons for closure
- Outcome at closure using items with the Supporting Families Outcome Framework⁹¹

Keyworker outcome measures

Data for the final two outcome measure (changes in professional wellbeing and changes in systemic practice) will be collected from all keyworkers in the study local authorities via an online survey emailed to them at the start of the trial and at the end of the study.

⁹⁰

https://assets.publishing.service.gov.uk/media/62471c2be90e075f08be4248/Annex_A_National_Supporting_Families_Outcome_Framework.pdf

⁹¹

https://assets.publishing.service.gov.uk/media/62471c2be90e075f08be4248/Annex_A_National_Supporting_Families_Outcome_Framework.pdf

Keyworkers in the intervention group will also be asked questions on these measures in a post-training survey.

Compliance and fidelity

Steps will be taken to monitor compliance and identify risks to contamination. The local authority level randomisation design has the advantage of making risks to contamination low as the model to embed systemic practice will only be implemented in intervention local authorities. In addition, local authorities in the trial are not geographical neighbours, meaning it is unlikely that families will move from one to another.

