Annex A – High-level timeline

Systemic practice pilot timeline

August 2024

- MOU and DSA signed — *Coram*

September 2024

- Ethical approval given — *Coram*

October 2024 – April 2025

- Pilot starts: IFT training (1-day intro for all staff and 5 days training for all keyworkers) — *IFT / Local Authorities*

November 2024 – April 2025

- Pre-training survey of keyworkers — *Ecorys / Coram*

January 2025

- Start of outcome data collection with families by keyworkers — *Local Authorities*
- Drop-in sessions for keyworkers and LA staff working on the Pilot begin — *Coram*
- IPE and qualitative data collection (interviews, observations) begins — *Coram*

April – June 2025

- Post-training survey of keyworkers — *Ecorys / Coram*

April – October 2025

- Additional 10 days training for identified ‘systemic champion’ keyworkers — *IFT*

February 2026

- End of baseline outcome data collection with families by keyworkers — *Local Authorities*

End April 2026

- End of midline and endline outcome data collection with families by keyworkers — *Local Authorities*

April – May 2026

- Post-pilot survey of keyworkers — *Ecorys / Coram*

May 2026

- Outcome data matching with LA data on families — *Local Authorities / Coram*
- Control group local authorities receive training — *IFT*

End May 2026

- Final administrative data to Coram — *Local Authorities / IFT*

June 2026

- Coram data clean and QA — *Coram*

August 2026

- IPE and outcome data analysis — *Coram*

Autumn 2026

- Draft final report to DfE — *Coram*
- Final published report — *DfE*

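### Step-up and positive progress are defined only in families whose support is ending, so the comparison depends on closure, which the intervention may itself change

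*Protocol*

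**What the plan says.** Tables 6 and 7 give both administrative family outcomes the same sample, "Families where keyworker support is ending", and the same time point, "At closure when the keyworker stops working with a family". Each outcome is one category of the reason for closure: "Step up/escalated to statutory children’s services" for step-up and "End of casework, positive progress made against all issues" for positive progress.

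Under Research questions, question 3 asks whether step-up falls for families with a keyworker. Question 4 asks whether there are "more case closures with positive progress" among families with a keyworker. Neither is limited to closed cases.

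Under Supporting Families Data collection, the assessment return includes the date the assessment started. The closure return lists Family ID, "Reasons for closure" and outcome at closure, with no closure date. For the Family Outcome Questionnaire, endline is at closure "or when the trial ends". That alternative is given for the questionnaire scores and not for the two administrative outcomes.

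Annex A ends baseline collection in February 2026. The end-April 2026 entry reads "End of midline and endline outcome data collection with families by keyworkers". Final administrative data reach the evaluator at the end of May 2026.

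**The concern.** Closure is not a baseline characteristic. It follows allocation, and question 4 treats one kind of closure as the effect sought. If systemic practice shortens or lengthens keyworker support, the families closed by the data cut-off are differently selected in the two arms, and randomisation no longer protects a comparison among them.

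Step-up is itself a closure reason, so step-up events are counted when they close a case. What goes missing is the open families with no event yet, and they go missing from the denominator only. Two arms with the same step-up risk among all families can then show different rates, and a real difference can disappear. Questions 3 and 4 rest on these two outcomes, which are the only family outcomes not self-reported with the keyworker present.

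**Working it through.** **1. Sample against question.** Questions 3 and 4 concern families with a keyworker. Tables 6 and 7 concern families whose support is ending. The two groups coincide only if every enrolled case has closed by the data cut-off. The Analysis section does not restore the open cases. It promises intention-to-treat, but for participants who provide outcome data, and an open case has no reason for closure.

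**2. Are open cases likely?** A family with a baseline in February 2026 has three to four months until the end of May 2026, and less if the extract is cut earlier. The Protocol puts the midline review typically at two to five months, and closure usually follows review. Some late entrants will probably be open. The Protocol gives no case length, so the share cannot be calculated.

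**3. Effect on the proportion.** Let r be the events as a share of all enrolled families and c the share closed. Then

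closed-only rate = r / c.

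With the same r in both arms, the true ratio is 1.00 and the closed-only ratio is c(control) / c(intervention). All rates below are assumptions.

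| Event, r in both arms | Closed, control v intervention | Closed-only, control v intervention | Difference (points) | Ratio |
|---|---|---|---|---|
| Step-up, 10% | 60% v 50% | 0.10/0.60 = 16.7% v 0.10/0.50 = 20.0% | +3.3 | 1.20 |
| Step-up, 10% | 70% v 60% | 14.3% v 16.7% | +2.4 | 1.17 |
| Step-up, 10% | 60% v 55% | 16.7% v 18.2% | +1.5 | 1.09 |
| Step-up, 10% | 70% v 80% | 14.3% v 12.5% | −1.8 | 0.875 |
| Positive closure, 45% | 70% v 80% | 64.3% v 56.25% | −8.0 | 0.875 |

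The sign depends on which arm closes faster.

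**4. Competing-events check.** Assume constant monthly hazards in the control arm: step-up 0.02, positive closure 0.08, other closure 0.04, total H = 0.14. Assume follow-up uniform from 2 to 15 months. The 15 months is the trial length in Table 10; the lower limit and the shape are assumptions. Then

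share closed = 1 − [exp(−2H) − exp(−15H)] / (13H).

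For control this is 1 − (0.756 − 0.122)/1.82 = 65.2%. Each event's share of all families is its hazard divided by H, times the share closed. Its share of closed families is its hazard divided by H.

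| Scenario | Closed | Step-up, all | Step-up, closed | Positive, all | Positive, closed |
|---|---|---|---|---|---|
| Control | 65.2% | 9.3% | 14.3% | 37.3% | 57.1% |
| Positive-closure hazard × 1.5 | 73.1% | 8.1% | 11.1% | 48.7% | 66.7% |
| All hazards × 1.25 | 72.2% | 10.3% | 14.3% | 41.3% | 57.1% |

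In the second row the step-up hazard is unchanged, yet closed-only step-up falls by 3.2 points, against 1.2 points among all families. In the third row the closed-only figures do not move, although positive closures among all families rise from 37.3% to 41.3% and step-up from 9.3% to 10.3%.

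The third row also shows that changing the denominator alone is not enough. Over unequal follow-up, the all-family proportion rises merely because everything happens sooner, so it mixes speed of closure with risk.

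**The case against.** **The Sample row may not define a denominator.** In Tables 3 to 5 that row says who is given the measure, and the Protocol nowhere speaks of a proportion of closed cases. The full strategy is left to a statistical analysis plan that is not at hand. This carries some weight, but the row is the only analysis population stated for these outcomes, the measure exists only at closure, and no end-of-trial alternative is given. It is a stated sample rule and not an omitted detail.

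**Question 4 may mean a better mix of closures.** Table 7's variable, progress at closure, allows that reading. The mix is still conditional on closing, and the objection does not help question 3.

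**Precision swamps the bias.** Borrow the local-authority ICC of 0.1 and the 361 and 199 families of Table 2 (both assumptions for these outcomes). With 50% and 60% closed, about 180.5 and 119.4 families remain, roughly 30 per authority, so the design effect is 1 + 29 × 0.1 = 3.9. The standard error is √[3.9 × (0.20 × 0.80/180.5 + 0.167 × 0.833/119.4)] ≈ 0.089. The illustrated 3.3 points is about 0.4 of that. This limits what is at stake in the pilot. The bias would not shrink with sample size, however, if the definition passed to a full trial.

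Four stronger readings are tempting and are not supported:

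- *Administrative follow-up stops on 30 April 2026.* That date covers the questionnaires; administrative data have their own end-May entry.
- *Cases cannot be placed in time at all.* The assessment start date is collected, the closure questionnaire records length of work with the family in broad bands, and the Analysis section anticipates a term for time from randomisation. These are coarse or partial substitutes for a closure date.
- *These are the only outcomes not self-reported in front of the keyworker.* That is true of family outcomes only; the two keyworker outcomes come from an emailed survey.
- *Many cases will be open and the bias has a known direction.* No closure or step-up rate is given.

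**Conclusion.** The point holds. As defined, both outcomes condition on a post-allocation event that the intervention may change, and they do not match the populations in research questions 3 and 4. A closed-only comparison can create a difference between arms or hide one.

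The size and direction cannot be derived from the Protocol. The illustrated shifts in step-up, from 1.8 points down to 3.3 points up with no true difference, rest wholly on assumed step-up and closure rates. The problem needs two conditions: some cases open at the cut-off, which the timeline makes likely, and a pattern of closure that differs between arms, which is plausible but not shown.

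The priority is moderate. These are secondary outcomes of a pilot seeking indicative evidence, and neither enters the progression criteria in Table 13.

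**What to change.** - Restate the sample in Tables 6 and 7 as all enrolled (consented) families.
- Add the closure date to the closure return.
- Analyse step-up and positive closure by a fixed time from the assessment start date already collected, or as competing events with open cases censored at the actual cut-off of the administrative extract. State that cut-off, and do not take 30 April 2026 by default.
- Do not change the denominator without also fixing the horizon or modelling time.
- Report closure rates by arm, and keep the closed-case proportions as descriptive figures.

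The cost is one extra date field from the local authorities and modest additional analysis. No further contact with families is needed.
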